4.3 Tertiary Objectives

To determine if long-term changes in Quality of Life scores [(the RAND-36 Health Survey, Disability of the Arm, Shoulder, and Hand (Quick DASH) questionnaire, and Breast-Q scores)] differ between women undergoing bilateral mastectomy followed by bilateral immediate tissue expander breast reconstruction randomized either to ropivacaine- (treatment) pre-operatively placed paravertebral blocks or subcutaneous paravertebral saline (placebo) injections.

5. Investigational Plan

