10.2 Study Design

Descriptive statistics for all outcome data (primary, secondary, and tertiary) will be calculated for each treatment group (ropivacaine or placebo), for each time point (days 1-3, day 90, year 2 and year 4). Student's t-test or Wilcoxon rank sum test will be used to compare the 2 treatment groups with regards to continuous or ordinal (approximately continuous) data, based on the distribution of the values (normally distributed or not normally distributed). Also change from baseline to each time point (follow-up) will be calculated for each outcome. The distributions of these "change values" will be analyzed in the same manner (depending on distribution). P-values less than 0.05 will be considered statistically significant for the primary outcome.

Longitudinal methods will be used to examine trends in scores, and changes in scores over time.

Opioid use also will be analyzed. IV morphine delivered via a Patient Controlled Analgesia pump during the first 24 hours of post-operative hospitalization will be recorded. Oxycodone and Tylenol taken by the patient after the first 24 hours until post-operative day seven will be recorded by the patient unless the patient is still hospitalized, in which case it will be recorded in the patient's medical record and abstracted by study staff. Answers to pain questionnaires and information regarding analgesic use will be verified by daily telephone calls to the patients by study staff. A common "pain unit" will be developed to standardize the various methods of opioid administration. Survival analyses will be used to compare time to opioid use, and time to stopping of opioid use. Descriptive statistics will be used to quantify amount and timing of opioid use, as well as proportion of patients requiring opioids post-operatively.

Furthermore, we will use the DASH survey, BREAST-Q[®], and the RAND-36 to determine the amount of functional long-term differences (3 months, 2 and 4 years after surgery) between treatment groups. These surveys will be used to compare the functional use of the arm before surgery to its use three months after mastectomy with immediate reconstruction.

Adverse events will be quantified and proportions of patients in each treatment group with different specific types of adverse events will be compared for safety data. Chi Square tests or Fisher's Exact Tests will be used to compare the proportions of patients with adverse events.

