10.3 Sample Size and Accrual

We expect that it will take 24 months to collect data on all patients through Day 90. Assuming a placebo effect of 30%, we would anticipate a true difference of 1.5 VAS units between the two groups. A true difference between scores of 4.1 to 2.6 would be clinically significant since it would bring a patient from the "moderate" down into the "mild" pain category. Thus a total of 70 patients will enter this placebo-control parallel-design study. The probability is 90 percent that the study will detect a treatment difference at a two-sided 0.05 significance level. This is based on the assumption that the standard deviation of the response variable is 2.5.

10.4 Interim Analyses for Efficacy.

A total of two interim analyses for efficacy will occur after the enrollment of 28 (40%) and 42 (60%) patients, giving a total of 3 'looks' at the data including the final analysis at 70 patients enrolled. Because of the small sample size in the first and second interim analyses, we will test for the equality of static pain scores at 6 hours post-surgery by treatment group using the Wilcoxon rank sum test. This statistical test considers the rank of the pain scores without regard to the distribution of these outcome measures; however, the test of significance uses a Z-score, which has a standard normal distribution.

In order to control for the overall type I error for the three proposed analyses, we will use a group sequential approach that utilizes the O'Brien-Fleming (1979)²⁷ alpha spending function. The critical Z-values for the Wilcoxon rank sum test assuming O'Brien-Fleming boundaries were determined by the STATA command 'landemets', which calculates these boundaries following the method of Lan and DeMets (1983)²⁸. Table X below gives the critical Z values and corresponding alpha levels at each analysis required to reject the null hypotheses of equality of pain scores by treatment group. In this null hypothesis, we consider a two-sided test which makes no assumption about the direction of the effect (e.g. placebo patients could potentially have a lower mean pain score than those on the intervention).

Table 5: Critical Z values and corresponding alpha levels for test the null hypothesis that static 6 hour post-surgery pain scores are equal among treatment groups.

Analysis number	Proportion of total N	critical Z to reject H0	Alpha(i) level
1	0.4	3.36	0.00079
2	0.6	2.68	0.0076
3	1.0	1.98	0.05

References

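### Quality-of-life scales are to be tested as scores and again as changes from baseline; one baseline-adjusted comparison per time point would be more precise, and section 10.2 should confirm the 6-hour score as the only primary test

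*Combined protocol and SAP*

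**What the plan says.** Section 10.2 covers primary, secondary and tertiary outcomes together. For continuous or ordinal data, "Student's t-test or Wilcoxon rank sum test will be used to compare the 2 treatment groups", the choice depending on the distribution. It continues: "Also change from baseline to each time point (follow-up) will be calculated for each outcome". The change values "will be analyzed in the same manner (depending on distribution"). The next sentence sets the threshold: "P-values less than 0.05 will be considered statistically significant for the primary outcome". One further sentence is relevant: "Longitudinal methods will be used to examine trends in scores, and changes in scores over time". It gives no model, covariates or outcomes.

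The tertiary objective in section 4.3 is "To determine if long-term changes in Quality of Life scores" and whether they differ between arms. Section 5.1 and the calendar in section 6 collect RAND-36, QuickDASH and the pre-operative BREAST-Q before surgery, and all three instruments again at Day 90, Year 2 and Year 4.

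For the primary outcome, section 10.1.1 describes a comparison of scores 6 hours after surgery. Section 10.4 gives the critical values "required to reject the null hypotheses of equality of pain scores by treatment group", and the caption of Table 5 names the static 6-hour pain score. The final critical value is 1.98.

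**The concern.** Two tests of the same scale at the same visit give two estimates and two p-values, and 10.2 does not say which is the result. For quality of life they also answer slightly different questions in a small trial. The score test ignores the baseline. The change test subtracts all of it, which adds noise unless follow-up tracks baseline closely. A model that estimates how much of the baseline to remove uses the same data and is at least as precise as either. With at most 35 patients per arm, that precision is worth having.

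For the primary outcome the issue is alignment. The single 0.05 rule directly follows the sentences on change values, and the Patient Pain Assessment Questionnaire, which includes static pain, is completed before surgery. Read alone, 10.2 does not say that a change analysis of static pain has no part in the primary decision.

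**Working it through.** **1. The plan's own figure.** The plan gives no precision figure for the quality-of-life comparisons. Its error-control figures do reproduce: with boundaries 3.36, 2.68 and 1.98 at 40%, 60% and 100% of 70 patients, the overall two-sided error is 0.050. The final value of 1.98 corresponds to a nominal p of 0.0477. A flat 0.05 at the last look would give 0.0524 overall.

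**2. Which scales have a usable baseline.** RAND-36 and QuickDASH use the same form before and after surgery. In BREAST-Q (Appendices C and D), three blocks carry the same items: psychosocial (10 items), chest and upper body (16) and sexual (6). Satisfaction with breasts does not match: 4 items before surgery, 16 after.

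**3. Precision for these scales.** Let r be the correlation of baseline with follow-up and k the baseline SD divided by the follow-up SD. The documents give neither; r = 0.3 to 0.7 and k = 1 are assumptions. Relative to the score test, the variances of the treatment difference are:

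- score: 1
- change: 1 + k² − 2rk, which is 2(1 − r) at k = 1
- ANCOVA: 1 − r² (large-sample; the small cost of estimating the slope is left out)

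Score minus ANCOVA is r², and change minus ANCOVA is (k − r)². Neither can be negative, so equal SDs affect the size of the gain but not its direction. At k = 1 the ratio ANCOVA/change is (1 + r)/2.

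| r | Score | Change | ANCOVA | ANCOVA below score | ANCOVA below change |
|---|---|---|---|---|---|
| 0.3 | 1 | 1.40 | 0.91 | 9% | 35% |
| 0.5 | 1 | 1.00 | 0.75 | 25% | 25% |
| 0.7 | 1 | 0.60 | 0.51 | 49% | 15% |

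As patients needed for the same precision, the score test needs 1/0.91 = 1.10, 1/0.75 = 1.33 and 1/0.51 = 1.96 times as many as ANCOVA. The change test needs 1.40/0.91 = 1.54, 1.00/0.75 = 1.33 and 0.60/0.51 = 1.18 times as many.

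With all 35 per arm followed (no dropout rate is stated), the 95% CI half-width in SD units is 1.96 × √(2/35 × variance). That is 0.47 for the score test. For the change test it is 0.55, 0.47 and 0.36, and for ANCOVA 0.45, 0.41 and 0.33, at r = 0.3, 0.5 and 0.7.

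**4. Primary outcome: what would happen if a change test could also be claimed.** The follow-up SD is 2.5 (section 10.3) and the critical value is 1.98, at the final analysis only. With baseline SD s, the two test statistics have correlation (2.5 − r·s)/√(2.5² + s² − 2·r·s·2.5). The chance under the null that at least one exceeds 1.98 in absolute value, from the bivariate normal, is:

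| Assumed baseline SD | r = 0 | r = 0.5 |
|---|---|---|
| 0.25 | 5.22% | 5.18% |
| 0.5 | 5.65% | 5.62% |
| 1.0 | 6.44% | 6.55% |
| 2.5 | 7.95% | 8.67% |

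One test alone gives 4.77%. At SD 2.5, r = 0.7 would give 8.94%.

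**The case against.** The strongest reply concerns the primary outcome. A reader might infer from 10.2 that the primary result has two p-values, either of which may be claimed, so that the boundary in 10.4 no longer protects the 5% level. The documents do not support that. Section 10.1.1 compares scores, 10.3 is powered on a difference in scores, and Table 5 states the null hypothesis as equality of 6-hour scores at all three looks. The time points listed in 10.2 do not include 6 hours. Nor is the baseline counterpart clear: Appendix A has an eight-item static pain block and a separate rating of current pain, and nothing says which supplies the 6-hour score. This reply stands. What remains is that 10.2 does not itself say the change analysis is supportive.

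A reader might also take 10.2 to mean that every outcome is in effect tested twice. That is too broad. Section 5.2.2 requires zero baseline opioid use, so change equals score, and length of stay has no baseline.

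On quality of life, both planned tests are valid under randomization, change matches the wording of the objective, and the 0.05 rule covers only the primary outcome. So this is not an error-rate breach. It is lost precision and two competing results. The longitudinal methods might adjust for baseline, but as written they commit to nothing and do not replace the two tests.

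**Conclusion.** The point holds for RAND-36, QuickDASH and the item-matched BREAST-Q scales: two tests are planned where one baseline-adjusted comparison would be more precise. The direction does not depend on the correlation or on equal SDs. The size does: 9% to 49% lower variance than the score test and 35% to 15% lower than the change test, for assumed correlations of 0.3 to 0.7 and equal SDs. It is a free improvement to tertiary analyses, not a threat to their validity.

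For the primary outcome only an alignment point remains. Error at the final look would exceed 5% only if a change test could also be claimed, which 10.1.1 and 10.4 do not allow for. Even then the amount rests on a baseline SD that the documents do not give: about 5.2% at an assumed SD of 0.25, and about 8.7% at an assumed SD of 2.5 with correlation 0.5.

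**What to change.** In section 10.2:

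1. For RAND-36, QuickDASH and the item-matched BREAST-Q scales, replace the score test and the change test with one ANCOVA per scale and time point: follow-up score on treatment and baseline score, reporting the adjusted difference with its 95% CI. Baseline-adjusted differences still address the tertiary objective, since at a given baseline a difference in follow-up score equals a difference in change. If the longitudinal methods are kept, name the model and how baseline enters it.
2. State that the 6-hour static pain score, as defined in 10.1.1 and 10.4, is the only primary test, judged at the final Table 5 boundary (Z = 1.98) in place of the flat 0.05, and that any change-from-baseline analysis of static pain is supportive.

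The cost is wording only: fewer tests, no new data, and no change to visits or sample size.

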8.1 Protocol Amendments

Any changes to the protocol will be made in the form of an amendment and must be approved by the IRB prior to implementation.

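### The p<0.05 cut-off for the primary outcome in section 10.2 does not match Table 5's final boundary (|Z| ≥ 1.98, two-sided p about 0.0477), and Table 5's alpha column hides the difference

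*Combined protocol and SAP*

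**What the plan says.** Section 10.2 (Study Design) gives the decision rule for the primary outcome: "P-values less than 0.05 will be considered statistically significant for the primary outcome". It does not mention interim looks and does not refer to section 10.4.

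Section 10.4 (Interim Analyses for Efficacy) sets a group sequential design for static pain at 6 hours, the measure that section 10.1.1 gives for the primary objective.

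- Timing: "A total of two interim analyses for efficacy will occur after the enrollment of 28 (40%) and 42 (60%) patients". This makes three looks "at the data including the final analysis at 70 patients enrolled".
- Purpose: "In order to control for the overall type I error for the three proposed analyses", section 10.4 adopts O'Brien-Fleming-type alpha spending by the Lan-DeMets method.
- Thresholds: Table 5 "gives the critical Z values and corresponding alpha levels at each analysis required to reject the null hypotheses". The rows are 3.36 with 0.00079, 2.68 with 0.0076, and 1.98 with 0.05. The table title also pairs the critical Z values with "corresponding alpha levels for test the null hypothesis that static 6 hour post-surgery pain scores are equal".

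Section 10.3 uses 0.05 as the design level: the study "will detect a treatment difference at a two-sided 0.05 significance level".

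**The concern.** The plan holds two rejection rules for one test at one analysis. Under section 10.2 the final result is significant if p<0.05, which on the normal scale is |Z|>1.96. Under Table 5 it is significant only if |Z| ≥ 1.98.

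Someone who turns to Table 5 to settle this finds 0.05 again, described as the level for rejection at the third analysis. But 1.98 and 0.05 cannot both be the per-analysis threshold, because a two-sided 0.05 corresponds to 1.96.

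Two things are at stake. If section 10.2 is followed at the final look, overall type I error goes slightly above the 5% that section 10.4 sets out to hold. And if the final p falls between the two thresholds, the trial's main conclusion depends on a choice between rules made after the data are seen.

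**Working it through.** **Inputs.** From section 10.4 and Table 5: looks at information fractions 0.4, 0.6 and 1.0 (28, 42 and 70 patients), a two-sided test, and printed Z values 3.36, 2.68 and 1.98. From section 10.3: difference 1.5, SD 2.5. From the Protocol Summary: 35 per arm. All figures use the normal approximation.

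**1. Reproduce Table 5.** The O'Brien-Fleming-type spending function at two-sided 0.05 is α(t) = 4[1 − Φ(z/√t)], where z is the upper 1.25% point of the standard normal. The boundaries come from recursive numerical integration.

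| Fraction | Cumulative alpha spent | Boundary Z | Nominal two-sided p at that Z | Table 5: Z, Alpha(i) |
|---|---|---|---|---|
| 0.4 | 0.00079 | 3.357 | 0.00079 | 3.36, 0.00079 |
| 0.6 | 0.0076 | 2.680 | 0.00736 | 2.68, 0.0076 |
| 1.0 | 0.0500 | 1.981 | 0.0475 | 1.98, 0.05 |

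Table 5 reproduces, so its Z values are correct for this design.

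**2. Identify the Alpha(i) column.** Row 1 cannot tell cumulative from nominal, because the two coincide at the first look. Row 2 can: the printed 0.0076 matches the cumulative value (0.00762) and not the nominal one (0.00736). The column is cumulative alpha, so the 0.05 in row 3 is the total spent over three looks and not a threshold for the final p-value.

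**3. Convert the printed Z values to p-values.** 2[1 − Φ(Z)] at 3.36, 2.68 and 1.98 gives 0.00078, 0.00736 and 0.0477. Against the Alpha(i) column, row 1 agrees, row 2 differs trivially, and only row 3 matters.

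**4. Overall type I error.**

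- Printed boundaries 3.36, 2.68, 1.98: 0.0502 (0.0500 with unrounded boundaries).
- Printed interim boundaries, final p<0.05: 0.0524.
- All three Alpha(i) entries used as p-value thresholds: 0.0525. Nearly all of the excess therefore comes from row 3.

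**5. How often the rules disagree.**

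- Under the null: 0.05237 − 0.05015 = 0.0022.
- At the protocol's inputs: SE = 2.5 × √(2/35) = 0.5976, and drift = 1.5/0.5976 = 2.510. The probability of rejecting is 0.7120 with a final p<0.05 and 0.7053 with 1.98, a difference of 0.0067.

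**6. The disputed zone on the pain scale.** For a comparison of means at that SD and size, 1.96 × 0.5976 = 1.171 and 1.98 × 0.5976 = 1.183. The zone is 0.012 points wide.

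**7. Z against t.** Section 10.2 allows a t-test. On 68 degrees of freedom |t| = 1.98 has p = 0.0518, which is looser than either rule; p = 0.0477 needs |t| = 2.016.

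**The case against.** The best reply is that section 10.4 already contains a correct final boundary. It counts the final analysis as the third look, says that overall error is controlled across all three, and gives 1.98 as the critical Z. It is the more specific rule, while section 10.2 is a general paragraph covering all outcomes and time points. Its 0.05 can be read as the overall level, as in section 10.3, and in a spending-function table Alpha(i) is naturally taken as cumulative. That is probably what was intended. But section 10.2 states 0.05 as a cut-off for p-values, no sentence calls it the overall level, and the lead-in to Table 5 calls the column the level for rejecting at each analysis.

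The size figures also rest on a normal approximation, whereas Table 5 is set up for the Wilcoxon test. In a simulation of the tie-corrected Wilcoxon test at 14, 21 and 35 per arm (assumption: normal scores, mean 4.1, SD 2.5, rounded and clipped to 0–10), overall error was about 0.0490 with Table 5 and 0.0513 with a final cut-off of 1.96, with simulation error about 0.0005. On that assumption the excess over 5% is nearer 0.1 than 0.24 percentage points. The gap between the rules is unchanged, at 0.0513 − 0.0490 = 0.0023. This supports calling the effect small, but does not remove the inconsistency.

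Two comments on the remedy are fair. The unrounded boundary is p = 0.0475, so 0.0477 carries the rounding in the printed 1.98. And the boundary assumes looks at exactly 40% and 60%. The caution about t statistics remains relevant, because section 10.4 justifies the Wilcoxon test only by the small interim samples and section 10.2 leaves the choice of test open.

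**Conclusion.** The concern holds and is minor. As written, section 10.2's threshold for the primary outcome disagrees with the final boundary in Table 5, and Table 5's alpha column, as described in the text, supports the wrong reading. The boundaries themselves are correct.

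The consequence is an overall type I error of 0.0524 in place of 0.0502, and a narrow band of p-values, 0.0477 to 0.05, in which the plan gives two answers. These figures assume approximate normality and looks at the planned fractions; the 0.67% and the 0.012-point zone also assume SD 2.5 and 35 per arm. The rejection probabilities of 0.7120 and 0.7053 serve only to compare the two rules. How they relate to the 90% power stated in section 10.3 is a separate question and does not affect the boundaries.

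**What to change.** - **Section 10.2.** Replace the quoted sentence with wording to this effect: *The overall two-sided type I error for the primary outcome is 0.05. At the final analysis, static pain at 6 hours is significant if the two-sided p-value is at most 0.0477 (|Z| ≥ 1.98), as in Table 5.*
- **Table 5.** Relabel Alpha(i) as cumulative alpha spent, add a column of nominal two-sided p-values (0.0008, 0.0074, 0.0477), and change the lead-in sentence to match.
- **Scale.** State the boundary as a nominal p-value, so that 1.98 is not applied to a t statistic.
- **Timing.** It is sensible to add that the boundary is recomputed from the spending function if the looks do not fall at 40% and 60%.

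The cost is a wording amendment, which under section 8.1 "will be made in the form of an amendment and must be approved by the IRB prior to implementation". Sample size and schedule do not change. There is no loss of power relative to Table 5. Relative to a final p<0.05 the loss is about 0.7 percentage points (0.7120 to 0.7053) at the protocol's inputs.

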APPENDIX E: RAND-36 ITEM SHORT FORM SURVEY	50
APPENDIX F: QUICK DASH QUESTIONNAIRE	54

List of Abbreviations

[figure not shown]
ADR	Adverse Drug Reaction
AE	Adverse Event/Adverse Experience
cc	Cubic Centimeter
CNS	Central Nervous System
CRF	Case Report Form
DASH	Disability of the Arm, Shoulder, and Hand
DATA	Device and Technique Assessment
DIEP	Deep Inferior Epigastric Perforator
HIPAA	Health Information Portability and Accountability Act
ICH	International Conference on Harmonization
ID	Identification
IRB	Institutional Review Board
IV	Intravenous
mg	Milligram
mL	Milliliter
PCA	Patient-Controlled Analgesia
PO	By Mouth (Latin: Per os)
POE	Provider Order Entry (System)
PSEF	Plastic Surgery Education Foundation
PSI	Pounds per Square Inch
RAND	Research and Development
SAE	Serious Adverse Event
SEER	Surveillance, Epidemiology, and End Results
TRAM	Transverse Rectus Abdominus Myocutaneous

1. Protocol Summary

Full Title	Use of Pre-operative Paravertebral Blocks to Decrease Post-operative Pain Following Mastectomy with Immediate Tissue Expander Reconstruction
Short Title	Paravertebral Blocks to Decrease Breast Reconstruction Pain
Study Type	Prospective, Randomized, Double-Blind Clinical Trial
Conducted By	The Department of Plastic and Reconstructive Surgery Johns Hopkins University School of Medicine
Principal Investigator	[name].
Sample Size	Enrolled: 70 (Randomization Treatment: Placebo = 35:35)
Study Population	
 • Women aged 18-75 years. • Choose bilateral mastectomy followed by immediate tissue expander breast reconstruction. • Have no inflammatory breast cancers. • Be aware of the nature of her malignancy. • Understand the study purpose, requirements, and risks. • Be able and willing to give informed consent.
Accrual Period	Two Years

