5.8 Justification For Placebo

In clinical trials of surgical interventions, sham procedure is an important scientific control. The sham paravertebral subcutaneous saline injections will contribute to isolate the specific effects of the treatment drug (ropivacaine hcl) as opposed to the patient's perception of having had a regular paravertebral block. Thus, sham paravertebral subcutaneous saline injections serve an analogous purpose to placebo drugs, neutralizing biases such as the placebo effect. Additionally, the subcutaneous paravertebral injections of placebo (normal saline) do not carry increased risks besides the potential risks of the injection process itself. The potential risks associated with the injection process itself include the risk of inadvertent vascular puncture (6.8%), pleural puncture (0.8%) and pneumothorax (0.5%),²⁶ all of which are classified as unlikely events (occurring in 1-10 of every 100 patients). Hence, the administration of placebo will strengthen the study design and any conclusion reached without significantly increasing the risk of complications.

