9.1 General

This study is collecting data regarding post-operative pain after a planned surgical procedure. The placement of the paravertebral block and ropivacaine is not expected to cause increased side effects or problems than those already anticipated with surgery. Subjects randomized to the placebo group will be at increased risk of harm related to the subcutaneous paravertebral saline injections without the chance of benefit. Any events that occur that are deemed "unexpected" to

the surgical procedure(s) performed, but related to the study procedures will be reported per current institutional requirements.

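### Section 10.2 compares adverse events between arms only by chi-square or Fisher tests, which at 35 per arm do not show how much excess harm remains possible; risk differences and confidence intervals should be added

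*Combined protocol and SAP*

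**What the plan says.** Section 10.2 (Study Design) of the combined protocol and SAP states that "proportions of patients in each treatment group with different specific types of adverse events will be compared for safety data". The method follows in the next sentence: "Chi Square tests or Fisher's Exact Tests will be used to compare the proportions of patients with adverse events". The section gives no rule for choosing between the two tests. Its only significance threshold, 0.05, is set for the primary outcome. It plans no risk difference, confidence interval or margin for harm, and it does not say how a non-significant comparison is to be read.

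The Protocol Summary gives 70 patients, 35 in each arm. The sample size in section 10.3 rests on the pain score alone.

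Two other sections bear on harm:

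- Section 5.8 (Justification For Placebo) says that the subcutaneous saline injections "do not carry increased risks besides the potential risks of the injection process itself". It then lists those process risks: vascular puncture 6.8%, pleural puncture 0.8% and pneumothorax 0.5%.
- Section 9.1 (General) says that "The placement of the paravertebral block and ropivacaine is not expected to cause increased side effects or problems than those already anticipated with surgery". It adds that placebo patients face added risk from their injections with no prospect of benefit.

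**The concern.** A test of equal proportions returns a p-value. It does not say how large an excess of harm the data leave open. With 35 patients per arm and events split by specific type, most comparisons will involve a handful of events, and most will be non-significant whether or not the block adds risk. The trial could then report that adverse events did not differ significantly while its own data remained compatible with an excess of ten percentage points or more. At stake is what the trial can say about harm. The primary efficacy result is not affected.

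**Working it through.** The plan states no power or precision for the adverse event comparison, so there is no figure of its own to reproduce.

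**Inputs.** n = 35 per arm (Protocol Summary). Event rate 6.8% (section 5.8). Assumptions: two-sided 0.05 for adverse event tests, and the rate in the other arm, which the documents do not give and which is varied below.

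**1. Smallest split that reaches significance.** With k events in one arm and none in the other, two-sided Fisher p = 2 × C(35,k) / C(70,k).

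- k = 5: 2 × 324,632 / 12,103,014 = 0.054, not significant.
- k = 6: 2 × 1,623,160 / 131,115,985 = 0.025, significant.

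The uncorrected chi-square statistic for k against 0 is 70 × (35k)² / (35 × 35 × k × (70 − k)) = 70k / (70 − k).

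- k = 3: 210/67 = 3.13, p = 0.077.
- k = 4: 280/66 = 4.24, p = 0.039, significant.

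Fisher therefore needs 6 against 0 and uncorrected chi-square needs 4 against 0. The two tests that the plan allows disagree at 4 and at 5 events.

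**2. Chance of missing a 6.8% event when the other arm has 0%.** Let X be binomial with n = 35 and p = 0.068, so the expected count is 35 × 0.068 = 2.38.

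- Fisher: P(X ≥ 6) = 0.029, so the miss rate is 97%.
- Uncorrected chi-square: P(X ≥ 4) = 0.212, so the miss rate is 79%.

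**3. Other assumed contrasts**, by exact enumeration of two independent binomials with 35 patients each:

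| Rates compared | Missed by Fisher | Missed by uncorrected chi-square |
|---|---|---|
| 6.8% v 0% | 97.1% | 78.8% |
| 6.8% v 0.5% | 97.5% | 81.7% |
| 6.8% v 3.4% | 99.0% | 92.3% |
| 13.6% v 6.8% | 93.8% | 83.4% |
| 0.8% or 0.5% v 0% | over 99.9% | over 99.9% |
| 6.8% v 6.8% | no difference to detect | no difference to detect |

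For an event at 6.8% in the higher arm, 0% in the other arm is the contrast easiest to detect. Against 0%, Fisher reaches 80% power at 35 per arm only for a true rate of about 22%. For 6.8% against 0% it would need about 115 per arm (searched in steps of 5).

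**4. What intervals would show from the same data.**

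- No events in one arm: exact two-sided 95% upper limit = 1 − 0.025^(1/35) = 10.0%. This does not exclude the 6.8% in section 5.8.
- 3 against 0: Fisher p = 0.24. The difference is 3/35 = 8.6 points, with a Newcombe 95% interval of −2.8 to +22.4 points.
- 5 against 0: Fisher p = 0.054. The difference is 5/35 = 14.3 points, with a Newcombe interval of +1.5 to +29.4 points.
- 0 against 0: Newcombe interval of −9.9 to +9.9 points.

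**The case against.** Four objections deserve an answer.

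**The 6.8% is not a risk of the ropivacaine arm alone.** Section 5.8 gives it as a risk of the injection process while justifying the placebo injections. A reader might infer that the planned test would miss a known 6.8% excess 97% of the time. The documents do not support that: the 0% comparator is an assumption, and both arms may carry the risk. This objection stands, and it limits the 97% to a stated contrast. It does not rescue the test. If both arms share the risk, a between-arm p-value says nothing about harm from either procedure, and per-arm rates with intervals are what is needed.

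**The plan does not treat non-significance as safety.** A reader might infer that it does, from section 9.1 together with the tests in 10.2. No sentence says so. There is no safety objective in section 4 or 10.1, no margin, and no threshold for adverse event tests. Section 9.1 gives an expectation that introduces event reporting; it is not a hypothesis to be tested. This stands. What remains is that the planned output cannot show how much harm is still possible.

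**Safety does not rest on these tests alone.** Events are counted and proportions given per arm, so a reader could work out an interval. Section 9.3 grades causality event by event, 9.4 covers reporting, and 9.5 provides for review by the principal investigator and annually by a committee. A needle complication can be recognised without a between-arm test. Nausea is also a secondary outcome with its own comparison. All of this stands, and it makes the point smaller. None of it is a planned between-arm estimate with its uncertainty.

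**Intervals will be wide at this sample size.** True: 0 against 0 still spans about ten points either way. But that width is the information a p-value leaves out.

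**Conclusion.** The point holds as a minor, cheap improvement. Chi-square or Fisher testing is the only formal between-arm analysis of adverse events generally, and no risk difference or interval is planned. At 35 per arm and an assumed two-sided 0.05, a 6.8% event is missed 97% (Fisher) or 79% (uncorrected chi-square) of the time against an assumed 0%, and 99% or 92% against an assumed 3.4%. With expected counts of about 1.2 per arm under pooling (2.38 / 2), Fisher is the likelier choice for such an event, but the plan does not say. If both arms carry the injection risk there is nothing for the test to find, and no events in an arm of 35 leaves up to 10.0% possible. These conclusions depend on the assumed threshold and comparator rates. The absence of any planned interval does not.

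**What to change.** Replace the sentence on chi-square and Fisher tests in section 10.2 with wording such as:

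> For any adverse event, any serious adverse event and each specific event type (including vascular puncture, pleural puncture, pneumothorax and hypotension), we will report the number and proportion of patients in each arm with exact (Clopper-Pearson) 95% confidence intervals, and the risk difference (ropivacaine minus placebo) with a 95% Newcombe or Miettinen-Nurminen interval. Fisher p-values will be descriptive only. A non-significant difference will not be read as absence of excess harm.

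One of the two interval methods should be chosen in advance. The cost is this wording and a few table columns, with no new patients or data. The downside is that the intervals will be wide and the safety statement will read less favourably than a list of non-significant p-values.
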